### **Data Analysis:**

Feasibility: The SCI Service at Miami VA actively serves approximately 300 patients. The Miami Project maintains a database of persons who have volunteered their participation in research studies and a database of individuals who have participated in past studies and volunteered additional participation. The database currently contains 3400 persons whose ages and levels of injury match the sought study participants. The Detroit VA SCI service oversees the care of greater than 100 patients/year. The Rehabilitation Institute of Michigan provides care for 350 SCI individuals. We anticipate completion of enrollment by the second quarter of Year 4, with 100 patients enrolled for PSG from each site.

Sample size justification and power: We will recruit 200 participants who meet our eligibility criteria and anticipate an SDB prevalence of 0.50 in SCI participants. This will allow us to randomize 100 participants with SDB to PAP or placebo arm. The neurocognitive test best characterized in both SCI and SDB is the Paced Serial Addition Test (PASAT). The PASAT is our primary study outcome. A mean difference in PASAT scores of 7 discriminates between those with and without cognitive impairment in populations with and without SDB. Assuming a standard deviation of 9 and alpha of 0.05, a sample size of 40 per study arm has a power of 0.93 to detect a mean difference of 7 units. Assuming a PAP non-adherence rate and/or loss to follow-up of 40%, we will continue to have sufficient power (81%) to detect such a difference with our proposed sample size of 100. These findings would be in keeping with PASAT values obtained in non-disabled patients with SDB vs. controls, and PASAT performance in other populations (e.g. multiple sclerosis, mild traumatic brain injury).

Planned analyses: We will score questionnaires while blind to PSG data and group allocation using instructions provided by the questionnaire developer. We will first examine continuous variables for normality. For those variables without a normal distribution, we will explore appropriate transformations in an attempt to achieve normality. Continuous variables will be summarized as means and SD, and categorical variables will be summarized as frequencies. Prevalence of poor SQ will be calculated as the proportion of individuals who complete the PSQI with a score of  $\geq 5$ .

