#### Primary Hypothesis (Specific aim 1, Hypothesis 1b)

A test of the primary null hypothesis, that PAP intervention does not increase mean PASAT score against the 1-sided alternative hypothesis that PAP intervention increases mean PASAT, will be based on a general linear model (GLM). PASAT score is modeled as a function of PAP intervention, using an indicator variable with 1 indicating PAP and 0 the sham treatment. A 1 degree of freedom test based on an F statistic will be used to test for a positive coefficient for the PAP indicator. This modeling approach provides a unified framework that accommodates covariates including use of sedating medications, years of education, level of injury, duration of injury, pain severity, presence of anxiety or depression, compliance with PAP, and recruitment center, each of which may reasonably be anticipated to influence PASAT score. We plan to include these covariates in our primary hypothesis test, which will be carried out at  $\alpha = 0.05$ . If the null hypothesis of no effect is rejected, computation of 95% confidence limits on the estimate of treatment difference in PASAT score mean will be carried out.

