#### Control of False Positive Rate of Inference

The inference of primary interest in this study is the effect of treatment on PASAT score. Because the test for intervention on PASAT is considered pre-planned, it will be carried out at  $\alpha$ -level 0.05. Similarly, tests for effects on groups of CV biomarkers, sleep, mood and quality-of-life measurements

are considered pre-planned in the sense that measurements in each group will be subjected to statistical testing regardless of test outcome for PASAT. Accordingly, tests for multiple measurements taken in each category of biomarkers will be carried out at  $\alpha$ -levels below 0.05. This approach recognizes that multiple testing is involved within each biomarker category and adjusts the significance level for individual tests downward to control the false positive inference rate at the category level. We will apply a False Discovery Rate (FDR) criterion of 5% separately for each category, thereby acknowledging the substantial overall number of tests per category but preserving power to detect true effects for each type of biomarker.

Primary analyses will be conducted in accordance with the intention-to-treat principle. We will also repeat analyses using a per protocol viewpoint. We will use statistical software, SPSS for Windows version 19 for all analyses.

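### Confidence limits for the primary PASAT difference are planned only after rejection of the null, so a non-significant trial has no committed interval for its primary effect

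*Combined protocol and SAP*

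**What the plan says.** The Primary Hypothesis section (Specific aim 1, Hypothesis 1b) tests the null "against the 1-sided alternative hypothesis that PAP intervention increases mean PASAT", in a general linear model with covariates, at alpha 0.05. The mechanism is: "A 1 degree of freedom test based on an F statistic will be used to test for a positive coefficient for the PAP indicator". The interval comes next, and it is conditional: "If the null hypothesis of no effect is rejected, computation of 95% confidence limits on the estimate of treatment difference in PASAT score mean" will then be done.

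That is the only mention of confidence limits in the document. The planned-analyses paragraph under Data Analysis offers means and SDs. The Secondary Hypotheses section plans two-sided between-group tests. The section on control of false positives repeats the level for PASAT ("Because the test for intervention on PASAT is considered pre-planned, it will be carried out at" 0.05), adds a false discovery rate rule for the other measures, and sets the analysis population: "Primary analyses will be conducted in accordance with the intention-to-treat principle".

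The sample size paragraph supplies the design difference ("A mean difference in PASAT scores of 7 discriminates between those with and without cognitive impairment"), an SD of 9, and the claim that "a sample size of 40 per study arm has a power of 0.93 to detect a mean difference of 7 units". It gives alpha as 0.05 without saying one- or two-sided.

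**The concern.** The condition is a stated rule, not an omission. Followed as written, it gives the primary endpoint an interval when the trial succeeds and none when it does not. A non-significant p-value alone does not tell the reader which gains remain plausible, and that is what a clinician deciding about PAP in chronic spinal cord injury would need after a null trial. Two null results can mean different things: one may sit around no effect, while another leaves most of the design difference open. Without a committed interval, whether the reader can tell them apart depends on a reporting decision taken once the result is known.

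**Working it through.** **Inputs.** SD 9, difference 7, alpha 0.05, 40 per arm and 40% non-adherence or loss come from the sample size paragraph. The total of 100 randomized 1:1 comes from the Randomization Protocol. Fifty per arm means no loss. Thirty per arm (100 × 0.6 = 60) is the extreme in which all of the 40% have no outcome; under intention-to-treat, non-adherent participants with outcomes stay in. True differences of 2, 3.5 and 5 are illustrative, because the documents give only 7. Everything is unadjusted; covariates would change the standard error and degrees of freedom.

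**1. The plan's own power.** SE = 9 × √(2/40) = 2.012, so the noncentrality is 7/2.012 = 3.478 on 78 df. Noncentral-t power is 0.930 for a two-sided 0.05 test and 0.964 for a one-sided 0.05 test. The stated 0.93 is therefore the two-sided figure. At 30 per arm, power is 0.842 two-sided or 0.909 one-sided. Neither is 81%, which two-sided corresponds to 27 to 28 per arm (0.801 and 0.815).

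**2. Thresholds and half-widths** (critical t × SE, unrounded values used):

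| | 50 per arm | 40 per arm | 30 per arm |
|---|---|---|---|
| SE = 9√(2/n) | 1.800 | 2.012 | 2.324 |
| t, one-sided 0.05 | 1.661 | 1.665 | 1.672 |
| t, two-sided 0.05 | 1.984 | 1.991 | 2.002 |
| Smallest significant gain, one-sided 0.05 | 2.99 | 3.35 | 3.88 |
| Half-width, two-sided 95% | 3.57 | 4.01 | 4.65 |
| F(1, df), 10% point | 2.757 | 2.771 | 2.794 |

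**3. Chance that no interval is planned** = 1 − power of the one-sided 0.05 test. For example, at 40 per arm and a true difference of 3.5, the noncentrality is 3.5/2.012 = 1.739, power is 0.532, and 1 − 0.532 = 0.468.

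| True difference | 50 per arm | 40 per arm | 30 per arm |
|---|---|---|---|
| 0 | 0.950 | 0.950 | 0.950 |
| 2 | 0.706 | 0.745 | 0.786 |
| 3.5 | 0.387 | 0.468 | 0.562 |
| 5 | 0.133 | 0.207 | 0.315 |
| 7 | 0.013 | 0.036 | 0.091 |

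**4. What the missing interval would show.** At 50 per arm, observed differences of −1.0 and 2.5 are both non-significant. Their 95% limits are −1.0 ± 3.57 = −4.57 to 2.57 and 2.5 ± 3.57 = −1.07 to 6.07. At 40 per arm, 2.5 ± 4.01 gives −1.51 to 6.51, which excludes 7. At the same size, 3.0 ± 4.01 gives −1.01 to 7.01, which does not. Both of these are non-significant too, since 3.0 is below 3.35.

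**5. Test against interval.** A one-sided 0.05 test with a 1-df F statistic rejects when the coefficient is positive and F exceeds its 10% point. A two-sided 95% interval includes 0 whenever the gain is smaller than its half-width. Gains of 2.99–3.57, 3.35–4.01 and 3.88–4.65 (50, 40, 30 per arm) would thus be significant with an interval that includes 0. The chance is the difference between the one-sided 0.05 and upper-tail 0.025 powers. At a true difference of 7 it is 0.987 − 0.971 = 0.016, 0.964 − 0.930 = 0.034 and 0.909 − 0.842 = 0.067. At the smaller differences tried it is at most about 13%.

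**The case against.** The best case for the plan is that little is lost. The model estimates the PAP coefficient whatever the p-value, nothing bars an interval, and planned means and SDs would let a reader rebuild an unadjusted one given the arm sizes. At full size, non-significance also nearly settles the 7-point question. At a true difference of 3.5 with SD 9, simulation shows that only 2% of non-significant trials at 50 per arm have a 95% interval that fails to exclude 7. The share is 18% at 40 per arm and 44% at 30. This limits the harm but does not remove the point. A rebuilt unadjusted interval is not the interval from the covariate model on which the inference rests. The 7 points are a design difference, not a stated smallest worthwhile benefit, so the whole interval matters.

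A reader might infer three stronger things that the documents do not support.

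- **That the level of the primary test is open.** It is not. The text gives a positive coefficient, a one-sided alternative and alpha 0.05, and contrasts PASAT with two-sided secondary tests. The 10% point of F follows; only the explicit rule is unwritten. Using the 5% point would give one-sided 0.025, against the declared level.
- **That test and interval are bound to conflict.** The sidedness of the limits is not stated. If they are two-sided, disagreement is confined to the narrow windows in step 5. Two-sided 95% limits beside a one-sided test are conservative reporting, not an error of coverage.
- **That the trial is underpowered.** The recomputed powers equal or exceed those stated.

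It is also fair to ask which estimate the interval would surround, since the covariate list includes PAP compliance, which is measured after randomization. That is a separate question about the model. Here it is enough that the interval belongs to the coefficient actually tested.

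**Conclusion.** The point holds, limited to reporting: the plan commits to an interval for its primary effect only after rejection. On unadjusted figures with SD 9, that leaves no committed interval in 95% of trials with no true effect, in 39/47/56% at an illustrative 3.5 points (50/40/30 per arm), and in 1/4/9% at 7. The validity of the test is not in question, but a null primary result would be harder to interpret than it need be, so the condition should go.

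The rejection rule and the possible test–interval disagreement are clarifications only. The power wording is secondary: 0.93 is a two-sided figure and the 81% does not reproduce at 30 per arm.

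**What to change.** 1. In the Primary Hypothesis section, delete the condition on rejection. Commit to reporting the PAP-minus-sham PASAT difference from the primary model with two-sided 95% limits whatever the test result. Note that the 7 points in the sample size paragraph are the design difference.
2. For clarity, state that the null is rejected when the PAP coefficient is positive and F exceeds its 10% point (2.76 at 98 df). Add that two-sided 95% limits may include 0 for a narrow range of significant results (3.35 to 4.01 at 40 per arm). A 90% interval, whose lower end matches the one-sided test, may be added but need not replace the 95% limits. At 40 per arm it would move the upper limit for an observed 3.0 from 7.01 to 3.0 + 3.35 = 6.35, so the 95% limits are the more cautious guide to what has been ruled out.
3. In the sample size paragraph, state that 0.93 is for a two-sided 0.05 test (one-sided 0.05 gives 0.964). Restate the 81% as 0.842 two-sided or 0.909 one-sided at 30 per arm, or give the arm size it assumed.

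The cost is wording only: no extra participants, data or power. It should be settled before unblinding, so that the form of the interval is not chosen with the result in hand.

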#### Secondary Hypotheses

A second phase of analysis will focus on CV biomarkers and measures of sleep quality, quality of life, mood and pain. These analyses are considered exploratory in nature and hence will benefit from comparisons within as well as between groups.

For within group contrasts, initial observations serve as baseline for assessing the effect of treatment at 4 months. As in a classical paired design, inference focuses on the difference between baseline and 4 month observations. Hence, individuals serve as their own control for an effect of intervention. The null hypothesis that the baseline does not differ from the 4 month measurement is tested using statistical methods for a paired design. For normally distributed measurements, a paired t test will be used. For variables that depart from normality and cannot be transformed to approximate normality, a Wilcoxon signed rank test will be used.

Comparisons between PAP and sham treatment groups at 4 months will be made based on the linear model described above for the primary endpoint. In contrast to PASAT, however, tests for treatment group differences of CV biomarkers and measures of sleep quality, HRQOL, mood and pain will be 2-sided. Because the number of secondary hypotheses to be tested is potentially large, these tests will be considered exploratory in nature. Accordingly, control of the false positive inference rate for these tests will be carried out at the group level, as described below, rather than for the entire set of secondary analyses. Similar approach will be taken for the analyses of select measures at the one month time-point.

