### Objectives/Specific Aims/Hypotheses

The proposal describes a multi-center double blinded, placebo controlled randomized trial (RCT) designed to examine the impact of SDB treatment in persons with chronic SCI. The **central hypothesis** is that the treatment of SDB with PAP will improve cognition, sleep quality, HRQOL, and CVD surrogate measures in persons with chronic SCI. The specific aims and hypotheses of the proposed research are:

Specific Aim 1	
Determine the associations between sleep disordered breathing (SDB) and cognitive impairments in chronic SCI and the impact of PAP therapy on cognitive measures in a cohort with chronic SCI and SDB.
 
Hypothesis 1a: Compared with patients without SDB, patients with SDB will exhibit more severe and widespread cognitive impairments (in memory, attention, and executive function), while controlling for depression, pain severity, duration of injury, level of injury, sedative use, and pre-morbid intelligence
 
Hypothesis 1b: SCI participants who are randomized to four months of therapeutic PAP will show improvement in cognitive measures (memory, attention, and executive function) compared with those receiving sham PAP.

Specific Aim 2	
Determine the impact of PAP therapy on surrogate CV biomarkers, sleep quality, quality of life, mood, and pain in a cohort with chronic SCI and SDB.
 
Hypothesis 2a: SCI participants randomized to four months of PAP will show an improvement in CV biomarkers (hs-CRP, TNF-a, VCAM-1, adiponectin, and 8-isoprostanate) compared with sham PAP.
 
Hypothesis 2b: Sleep quality, quality of life, mood, and pain will improve in SCI participants receiving PAP and stay the same or worsen in those randomized to sham PAP.

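### Hypothesis 2b has no stated deciding test: within-arm paired tests are presented as inference on PAP, and the planned PAP-versus-sham comparison is not given priority

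*Combined protocol and SAP*

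**What the plan says.** Two hypotheses sit under Specific Aim 2 and are worded differently. Hypothesis 2a, on the cardiovascular biomarkers, is a contrast between arms; it ends "adiponectin, and 8-isoprostanate) compared with sham PAP". Hypothesis 2b, on sleep quality, quality of life, mood and pain, makes one statement for each arm: these outcomes "will improve in SCI participants receiving PAP and stay the same or worsen in those randomized to sham PAP".

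The Secondary Hypotheses section then plans two kinds of analysis for all these outcomes, and gives this reason: "These analyses are considered exploratory in nature and hence will benefit from comparisons within as well as between groups".

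- **Within arm.** The 4-month value is set against baseline: "For normally distributed measurements, a paired t test will be used", with a Wilcoxon signed rank test as the fallback. The section gives this test a causal reading: "Hence, individuals serve as their own control for an effect of intervention".
- **Between arms.** "Comparisons between PAP and sham treatment groups at 4 months will be made based on the linear model described above for the primary endpoint". The section adds that "tests for treatment group differences of CV biomarkers and measures of sleep quality, HRQOL, mood and pain will be 2-sided".

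On multiplicity, the Control of False Positive Rate of Inference section says "We will apply a False Discovery Rate (FDR) criterion of 5% separately for each category". It does not say whether the paired tests count. No section says which of the two analyses decides 2a or 2b.

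**The concern.** A change from baseline within one arm is not an estimate of what PAP does relative to sham. It also contains placebo response, regression to the mean and time trends. The sham arm exists to remove these. The Intervention section gives both arms a device, a mask, instruction and telephone support, so shared improvement in self-reported sleep, mood, pain and quality of life is plausible.

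The wording of 2b invites a reader to look for a significant change on PAP and a non-significant one on sham. That pattern does not test 2b. A non-significant sham result with 30 to 50 participants does not show that sham stayed the same, and two arms that changed by the same true amount can easily fall on opposite sides of the 5% line. At stake is a reported benefit on patient-reported outcomes or biomarkers when the arms did not differ.

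**Working it through.** **1. The plan's own figure.** The documents give no error rate, power or expected change for the Aim 2 outcomes. The only figure of this kind is the PASAT power of 0.93 (40 per arm, difference 7, SD 9, alpha 0.05). It reproduces: the noncentrality is 7 / (9 × √(2/40)) = 7 / 2.012 = 3.48, and a 2-sided two-sample t test then has power 0.930. It concerns a between-arm test and does not bear on the paired tests.

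**2. Inputs.**

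- 50 per arm: 100 randomized 1:1 (Randomization Protocol; Sample size justification and power).
- 30 per arm: the same section allows 40% for non-adherence or loss, and 100 × 0.60 / 2 = 30.
- Each paired test is 2-sided at 0.05, counted in the direction of improvement (assumed level; the plan sets none for the paired tests).
- d, the true change in units of the SD of change, is the same in both arms, so PAP has no effect. Its size is an assumption, shown over 0 to 0.5.

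**3. Formula.** The chance that one arm shows a significant improvement is

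p = 1 − F(t₀.₉₇₅,ₙ₋₁), where F is the noncentral t distribution with n − 1 degrees of freedom and noncentrality d√n.

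The arms are independent, so the chance that PAP is significant and sham is not is p(1 − p). Example at d = 0.2:

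- 50 per arm: d√n = 1.414, p = 0.283, and 0.283 × 0.717 = 0.203.
- 30 per arm: d√n = 1.095, p = 0.184, and 0.184 × 0.816 = 0.150.

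| Common change d | p, n = 50 | PAP significant, sham not, n = 50 | p, n = 30 | PAP significant, sham not, n = 30 |
|---|---|---|---|---|
| 0 | 0.025 | 2.4% | 0.025 | 2.4% |
| 0.1 | 0.103 | 9.2% | 0.076 | 7.1% |
| 0.2 | 0.283 | 20.3% | 0.184 | 15.0% |
| 0.3 | 0.548 | 24.8% | 0.355 | 22.9% |
| 0.4 | 0.792 | 16.5% | 0.563 | 24.6% |
| 0.5 | 0.934 | 6.2% | 0.754 | 18.6% |

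The product p(1 − p) cannot exceed 0.5 × 0.5 = 25%. It reaches that at d of about 0.28 with 50 per arm and about 0.37 with 30 per arm.

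**4. Check by simulation** (40,000 trials per setting, equal true change in both arms). The direct test here is an unadjusted t test on the difference in change, which is simpler than the planned linear model.

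| n per arm, d | Pattern seen | Direct between-arm test significant | Direct test significant, given the pattern |
|---|---|---|---|
| 50, 0.28 | 25.2% | 5.1% | 10.0% |
| 50, 0.30 | 24.6% | 4.9% | 9.5% |
| 30, 0.30 | 22.9% | 4.8% | 10.6% |
| 30, 0.36 | 25.2% | 5.0% | 9.4% |

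The direct test keeps its 5% (about half of it in favour of PAP) whatever the common change is. Where the pattern appears, the direct test disagrees about nine times in ten, so it matters which one decides.

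**5. The between-arm model.** It is the one described under Primary Hypothesis. The covariates listed there are sedating medication, education, level and duration of injury, pain severity, anxiety or depression, PAP compliance and center. The outcome's own baseline value is not among them. Pain severity and anxiety or depression are listed without a time point, so something close to a baseline value may enter for pain and mood. For the sleep scales, quality of life and the biomarkers, the outcome's baseline enters only through the paired tests.

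**The case against.** The strongest reply is that the plan already contains the right test. Directly after the paired tests, the same section plans a 2-sided PAP-versus-sham comparison for every Aim 2 outcome. Its remarks on multiple testing follow that comparison and most naturally refer to it. If 2b is true, the arms differ, and that comparison would test the difference. The analyses are labelled exploratory, and the primary PASAT test is between arms.

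Much of this stands. A reader might infer that the plan discards the sham control; it does not. A reader might also infer that the plan adopts a rule under which PAP significant and sham not significant confirms 2b; no sentence says so. Nor is 25% the plan's error rate. It is a mathematical ceiling, it depends on an assumed common change, and it applies only if the between-arm result is set aside. The 30-per-arm case is a low count, because under intention-to-treat non-adherent participants who return stay in the analysis.

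Three things remain. The text attributes within-arm change to the intervention in so many words. Unlike 2a, Hypothesis 2b names no contrast with sham. The priority of the between-arm test has to be read into the plan, because it is not stated. The exploratory label does not turn a within-arm change into an estimate of PAP versus sham, and the next section also calls these tests pre-planned.

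**Conclusion.** The point holds as a gap in the decision rule and as an invalid reading given to the paired tests; it does not hold as a claim that Aim 2 lacks a controlled comparison. If 2b were judged by the pattern of significance and both arms truly changed equally, the false-positive rate per outcome would be 2.4% with no change, 7–9% at 0.1 SD of change, 15–20% at 0.2 SD and at most 25%, falling to 6–19% at 0.5 SD. This assumes independent arms, approximately normal changes, 30 to 50 analysed per arm, 2-sided paired tests at 0.05, and a common change whose size the documents do not give. Severity is modest: the outcomes are secondary and exploratory, and the primary conclusion is untouched.

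**What to change.** - Reword Hypothesis 2b as greater improvement with PAP than with sham.
- State that the planned PAP-versus-sham comparison at 4 months, adjusted for the baseline value of the same measure, is the only basis for treatment-effect conclusions in Aim 2, and that these are the tests that enter the 5% FDR in each category. Apply the same rule to the measures analysed at one month.
- Report within-arm changes as means with confidence intervals, described as change over time. Say that an interval excluding zero is not evidence of a PAP effect. Delete the statement that participants act as their own control for the intervention.

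The cost is wording in the analysis plan and one added model term. The baseline values are already collected (Biomarkers; Sleep, Quality of Life, and Mood), so no new data are needed. The downside is that within-arm p-values can no longer support an efficacy claim.
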